4.2 Study Endpoints

4.2.1 Primary Study Endpoints

The primary study endpoint is the change in Gpi functional connectivity from baseline (pre-sonication) to post-sonication. The change in functional connectivity will be compared between PLIFUS and sham conditions. This measure was selected because of our prior finding that increased Gpi functional connectivity is highly correlated with psychosis severity in schizophrenia and because Fallon and colleagues ¹⁴ demonstrated that a single session of PLIFUS decreased functional connectivity in macaques.

4.2.2 Secondary Study Endpoints

Secondary study endpoints are measures of clinical symptoms, which are assessed using the following scales: AHRS, DESA, BPRS, and PSYRATS. Safety assessments will consist of the Columbia Suicide Severity Rating Scale (C-SSRS), MoCA, and SAFTEE and addendum assessment for side effects.

5 Study Enrollment and Withdrawal

Participants will be individuals with a diagnosis of schizophrenia who report continuous psychotic symptoms (auditory hallucinations or delusions) of at least moderate severity. Participants may be taking antipsychotic

medication or be medication-free, must be free of unstable psychiatric or medical illness, cannot have suicidal ideation, or a history of violence or of suicidal behavior (attempts), cannot have epilepsy or be taking anticonvulsant medication and must have no contraindication to MRI or sonication, including metal implants.

5.1 Inclusion Criteria

1. Males and females 18 to 55 years of age, inclusive, at time of informed consent
2. Must report current psychosis, as defined by a score of ≥ 4 on at least one of the following psychosis items on the Brief Psychiatric Rating Scale (BPRS): suspiciousness, hallucinations, unusual thought content, or grandiosity. Psychosis has to have persisted continuously for at least 4 weeks.
3. Must have a diagnosis of either schizophrenia or schizoaffective disorder as established by a Structured Clinical Interview for DSM-V (SCID)
4. If taking antipsychotic medication, the dose must be unchanged for at least 4 weeks prior to randomization. If not taking antipsychotic medication, must be intending not to start medication until after completion of the study (approximately 3 weeks)—this decision must be judged to be appropriate by the research psychiatrist and by the participant's clinician.
5. If assigned female at birth and of childbearing potential, patients must
 - a. have a negative urine pregnancy test (all participants assigned female at birth regardless of childbearing potential will be required to submit a pregnancy test), and
 - b. not be nursing or planning a pregnancy for the duration of the study through 30 days after the last sonication visit, and
 - c. be abstinent or willing to use a reliable method of birth control from the Screening Visit and continue with the same method until termination from the study.

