4.1 Description of Study Design

This is a single-site, phase 2, sham-controlled random-order cross-over pilot trial of PLIFUS targeting the right Gpi in individuals with schizophrenia. Twelve individuals with schizophrenia who report continuous hallucinations or delusions of moderate or greater severity will receive one session of PLIFUS and one session of sham PLIFUS in random order, one week apart. If no effect of PLIFUS is detected on measures of functional connectivity or psychotic symptoms in the first 12 completers with good quality imaging data, the trial will be changed to 3 sessions of PLIFUS or sham administered over 5 days for 4 subsequent participants.

Potential participants will be enrolled at NYU Langone Manhattan, NYU Langone Brooklyn, and Bellevue Hospital. Recruitment-only procedures will occur at Manhattan Psychiatric Center (see section 5.5.3). Following informed consent, potential participants will be screened by a psychiatrist who will assess psychiatric and medical status. A Brief Psychiatric Rating Scale will also be administered to assess inclusionary status. Individuals who meet inclusionary and exclusionary criteria will then have a structural MRI performed at the MRI visit and with each fMRI scan at Intervention Visits 1 and 2 to guide neuronavigation of PLIFUS. The two sessions of PLIFUS/Sham will occur in random order, one week apart. Randomization schedule will be done using Matlab. Participants will first have an fMRI for measurement of right Gpi functional connectivity, preceded and followed by symptom rating scales. PLIFUS/sham will then be administered over 10 minutes, during which symptom ratings will again be recorded. Symptom ratings will be repeated 5, 30, and 60 minutes, 1 day and 7 days post-sonication/sham. fMRI will be repeated starting 10 minutes after sonication/sham. Safety assessments will be completed prior to discharge of participants 1 hour after each sonication/sham session and after 24-48 hours and 7 days.

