5.5.2 Bellevue Hospital

Staff can refer patients from the Bellevue Adult Outpatient Psychiatry Clinic (OPC), Inpatient Psychiatry Units, and Comprehensive Psychiatry Emergency Program (CPEP) who are appropriate for study participation and willing to speak to an investigator, by reaching out to the study team with the MRN. The study team will then access EPIC to determine the patient's initial eligibility. If the patient seems eligible based on their chart, a psychiatrist/psychologist/nurse practitioner on the study team will assess the clinical appropriateness of the individual to participate in research and capacity to consent.

Consent and screening procedures can take place in the CPEP or Inpatient Psychiatry Units for those in which it is applicable. Of note, no screening laboratory procedures (urine drug screen, urine pregnancy screen) will take place for those who are screening in the CPEP and/or Inpatient Psychiatry Units. Following screening procedures, individuals who qualify, and who are judged by their clinicians to be safe and appropriate for participation, but still remain an admitted to the hospital, will continue in the study once discharged. Outpatients recruited from Bellevue can start screening at the OPC (including collection of urine laboratory specimens if the patient prefers to meet there instead of [name] or the [name] Imaging Center), or can begin/finish screening either at [name] or the [name] Imaging Center.

Of note, study staff may also come across potentially eligible patients at NYU Langone Manhattan, NYU Langone Brooklyn, and Bellevue Hospital via chart review or by participating in rounds. Study staff would first reach out to the patient's treating physician to inquire about appropriateness for participation and permission to contact the individual if deemed fit for screening.

The time required to complete recruitment and consenting will be variable depending on availability of clinicians. Potential participants will be allowed as much time as is needed to consider participation, including discussing this with family and their clinician. All interactions with potential participants will take place in private rooms to maintain confidentiality. Any identifiable data of screen failures will be destroyed immediately after the recruitment period has ended.

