7.1.1 Study Specific Procedures

Assessments:

*Brief Psychiatric Rating Scale (BPRS)*⁴⁹: The BPRS is an 24-item scale that measures positive symptoms, negative symptoms, general psychopathology and affective symptoms. Individual items are scored on a seven point Likert scale. The BPRS has been extensively used in trials of antipsychotic agents and has been shown to be sensitive to change. Psychometric properties and the underlying factor structure are well-established. We will use a 1 week (7 day) lookback period for this clinical assessment.

*Buss-Perry Aggression Questionnaire (BPAQ)*⁴⁸:

The Buss-Perry Aggression Questionnaire consists of 29 items and contains 4 subscales: Physical Aggression, Verbal Aggression, Anger, and Hostility. The BPAQ will be administered at screening to assess a history of violence.

Structured Clinical Interview for the DSM-5 (SCID): The SCID for the DSM-V (Modules A-E) will be used to assess the primary psychiatric diagnosis for patients. The other modules for the SCID will not be performed as they do not relate to the inclusion/exclusion criteria.

Edinburgh Handedness Inventory (EHI)⁵⁰:

The EHI is a 10-item scale that measures laterality preferences when performing different tasks. Participants are asked to indicate which hand (right or left) they use when performing different actions. A laterality quotient is determined by calculating the percentage of activities that are completed solely with the right hand. A laterality score of 100 would reflect complete right-handedness. A score of 60% or greater will be used as the cutoff for right-handedness. Handedness will be recorded but is not an entry criterion.

Systematic Assessment for Treatment Emergent Side Effects (SAFTEE)⁵¹: The SAFTEE is a well-established and validated structured interview for assessment of side effects in intervention studies in schizophrenia. It consists of two components, an open-ended inquiry and a comprehensive review of all body systems.

An addendum to the SAFTEE will also be used to assess the following side effects that have been reported in other human subject ultrasound studies: mood deterioration, scalp heating, anxiety, neck pain, and pruritis (itching).

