7.2.2 Screening Visit (Days -30 to -1)

- Complete quiz documenting the subject's understanding of study procedures, risks and alternatives.
- Complete Assessment of Capacity
- Obtain written informed consent.
- Complete Consent Checklist to document that informed consent procedures have been followed (i.e., Key Information Sheet provided, all questions were answered by study staff, consent given prior to any procedures being performed, etc.)
- Complete a medical and psychiatric evaluation by a study psychiatrist, including history and physical examination and recording of medications.
- Complete the Buss-Perry Violence Questionnaire by a research assistant
- Obtain urine sample for pregnancy test and urine toxic screen
- The psychiatrist will also complete a Structured Clinical Interview for DSM5 (SCID) to establish a diagnosis of schizophrenia or schizoaffective disorder and to assess exclusionary diagnoses, including substance use disorders
- The study psychiatrist will complete the Columbia Suicide Severity Rating Scale (C-SSRS), MoCA, and CGI.
- A research assistant will complete the Brief Psychiatric Rating Scale (BPRS) to determine whether the candidate meets symptom severity criteria.
- Determine eligibility based on inclusion/exclusion criteria

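### The BPRS score that defines current psychosis is rated once at Screening and never re-applied before session 1, so an improved participant can be treated and add little to the symptom comparison

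*Combined protocol and SAP*

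**What the plan says.** Section 5.1 item 2 reads "Must report current psychosis, as defined by a score of ≥ 4 on at least one of the following psychosis items" of the BPRS (suspiciousness, hallucinations, unusual thought content, grandiosity) and adds "Psychosis has to have persisted continuously for at least 4 weeks". Section 7.2.2 places the rating at the Screening Visit, Day -30 to Day -1: "A research assistant will complete the Brief Psychiatric Rating Scale (BPRS) to determine whether the candidate meets symptom severity criteria". On the look-back, Section 7.1.1 says "We will use a 1 week (7 day) lookback period for this clinical assessment".

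The next scheduled BPRS is at the final visit (Sections 7.2.5 and 18), or at early termination (7.2.6). Intervention Visit 1 (7.2.4) has the CGI, C-SSRS, SAFTEE and PSYRATS before the first scan, and AHRS and DESA before sonication. None of these has an eligibility threshold.

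For Bellevue, Section 5.5.2 says "Consent and screening procedures can take place in the CPEP or Inpatient Psychiatry Units for those in which it is applicable"; people who are still admitted continue in the study after discharge. Section 4.1 describes who is treated: "Twelve individuals with schizophrenia who report continuous hallucinations or delusions of moderate or greater severity will receive one session of PLIFUS". Section 5.6 expects participation to last 14 to 21 days from consent to the last assessment.

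**The concern.** The criterion is worded in the present tense, but it is checked at a visit that may come well before treatment. Section 4.1 describes the people who receive sessions as at least moderately ill. Nothing in Sections 5.1, 5.8.1 or 7.2 secures that on Day 0. Section 5.8.1 lets the investigator end participation for a newly met exclusion criterion, but does not mention loss of an inclusion criterion.

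The Bellevue pathway makes a stale score more plausible, because the rating can be made during an acute stay and the sessions given after it. Screening laboratory tests are not done in those units, so part of screening falls elsewhere, yet nothing says the BPRS is repeated then.

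What is at stake is sensitivity on the symptom outcomes. A participant who is already mild on AHRS, DESA or PSYRATS has little room to fall in either session. Section 9 lists symptom severity among its primary outcomes, and Sections 6.1.8, 7.15 and 9 include a symptom effect size of 0.5, alongside fMRI, in the rule for moving to three sessions. The crossover and the baseline covariate keep the comparison fair, but they do not give back room to improve.

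**Working it through.** The plan has no power calculation or dilution estimate to reproduce. The check covers the timing and then the possible size of the effect.

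**Age of the score**
- Sections 7.2.2 and 18: Day -30 to Day 0 is 30 days. The latest session 2 is Day 8, so 30 + 8 = 38 days. With the 7-day look-back, a Day -30 rating describes about Day -37 to Day -30.
- Section 5.6: if the whole process takes at most 21 days and the final visit is Day 14 to 16 (7.2.5), Screening falls 21 - 16 = 5 to 21 - 14 = 7 days before Day 0. With Section 18's Day 13 to 15 the range is 6 to 8 days.
- The two timetables disagree: about a week, or up to 30 days.

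**Can the antipsychotic dose change between the rating and randomization?** Item 4 says "If taking antipsychotic medication, the dose must be unchanged for at least 4 weeks prior to randomization", and Section 18 puts randomization at the MRI Visit (Day -30 to -1). I listed every combination of Screening, randomization and dose-change day with the change on or after the rating and at least 28 days before randomization. Four exist:
- Screening -30, randomization -2, change -30
- Screening -30, randomization -1, change -30
- Screening -30, randomization -1, change -29
- Screening -29, randomization -1, change -29

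Under the 21-day maximum there are none.

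**Size of dilution.** Assumptions, none from the documents: the within-person PLIFUS-minus-sham difference is normal with mean 0.60 and SD 1 in symptomatic participants, and is exactly 0 in *k* of 12 who have improved. With f = k/12:
- mean = 0.60(1 - f)
- variance = (1 - f) + 0.36 f(1 - f)
- effect size d = mean / √variance
- chance of an observed effect of at least 0.5: noncentral t, 11 degrees of freedom, noncentrality d√12, evaluated above 0.5√12 (an approximation for a mixture)

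| k | mean | variance | d | chance of ≥ 0.5 |
|---|---|---|---|---|
| 0 | 0.600 | 1.000 | 0.60 | 64% |
| 1 | 0.550 | 0.944 | 0.57 | 60% |
| 2 | 0.500 | 0.883 | 0.53 | 56% |
| 3 | 0.450 | 0.818 | 0.50 | 51% |
| 4 | 0.400 | 0.747 | 0.46 | 47% |

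Direct simulation of the mixture gives 57%, 52% and 48% for k = 2, 3 and 4, so the approximation is adequate.

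**Sensitivity to what improved means**
- Improved participants have no effect but ordinary rating noise (SD 1): about 50%, 43% and 36% for k = 2, 3 and 4.
- Improved participants keep half their response (mean and spread halved): about 63%, 62% and 62%, against 64% with none improved.

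**The case against.** The best counter-argument is that the plan already limits the problem. Section 5.6 gives a maximum of 21 days, the Protocol Summary gives a participant duration of three weeks, and item 4 speaks of about three weeks. On that timetable the score is about a week old. Item 2 also requires four weeks of continuous psychosis, which selects people unlikely to remit quickly. Both points stand and lower the severity. Neither closes the gap: Section 5.6 states an expectation while 7.2.2 and 18 set the permitted window, and the persistence clause is not tied to Day 0.

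A reader might infer that item 4 generally lets people be rated, have their antipsychotic changed, and then be treated. The text does not support that. Before randomization it works only for Screening on Day -30 or -29. Item 4 says nothing about the time after randomization, but silence does not show that changes are expected, and the point does not rest on it.

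A reader might also infer that a stale score decides whether the three-session stage happens. It does not do so alone. The 4.2.1 primary endpoint is functional connectivity, symptoms are secondary in 4.2.2, the rule also uses fMRI, the DSMB must approve the switch, and all results are exploratory.

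Finally, a fall from 4 to 3 on a BPRS item is not the floor of AHRS, DESA or PSYRATS, and a drop from 0.60 to 0.46 (0.14) is less than half the sampling SD of an effect size at n = 12 (roughly √(1/12) ≈ 0.29). Both are fair. They are reasons to treat the dilution figures as illustrations.

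**Conclusion.** The point holds as a cheap improvement of low to moderate severity. The entry score is rated once, the permitted window is up to 30 days, acute-setting screening with treatment after discharge is allowed, and no rule re-checks severity before session 1. The plan therefore does not secure the population that Section 4.1 describes.

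The direction of the effect is clear: improved participants weaken the symptom comparison. Its size is not knowable from the documents. It depends on three assumed quantities: the true effect, the number improved, and how much response they keep. Across the cases examined, with a true effect of 0.60, the loss in the chance of reaching 0.5 runs from about 1 or 2 percentage points (half the response kept) to 17 points (four of 12 with exactly zero change), and to about 28 points (four of 12 with no effect but ordinary noise). The figures do not show that the trial will miss a real effect.

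**What to change.** In Section 5.1 item 2 and Section 7.2, require the score of at least 4 to hold on a rating of the four BPRS psychosis items made within 7 days before Intervention Visit 1. This can be done at the MRI Visit before randomization, if that visit falls inside the window, or on Day 0 before the first scan. Anyone who no longer meets the criterion is replaced before any session. A Screening BPRS already inside the window needs no repeat. Section 18 should show the rating.

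A Day 0 check comes after randomization as Section 18 now places it, so the text should say how the vacated sequence slot is reused. The check precedes any treatment and is made by a blinded rater, so it does not bias the comparison.

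Reconcile the 14-to-21-day duration in 5.6 with the 30-day window in 7.2.2 and 18.

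Cost: a short amendment, about 10 minutes of existing rater time for people screened early, and a few more screen failures before treatment. No visit or staff is added. A 7-day look-back does not guarantee room to fall on momentary ratings, so a pre-specified sensitivity analysis in those still symptomatic on the pre-session AHRS, DESA or PSYRATS would be a useful complement and needs no new data.

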5.2 Exclusion Criteria

1. Current substance abuse / dependence for substances other than nicotine and THC, (i.e. alcohol, amphetamines, barbiturates, etc.)
 - a. A positive urine toxicology screen (excluding THC, tricyclic antidepressants, or benzodiazepines (if prescribed)).
 - b. Moderate or severe cannabis use disorder.
2. Diagnosis of major mood disorder or other Axis I disorder other than schizophrenia or schizoaffective disorder as determined by a SCID
3. Current or recent suicidal ideation – suicidal ideation with intent or plan (indicated by affirmative answers to items 4 or 5 of the Suicidal Ideation section of the baseline C-SSRS) in the 6 months prior to screening or have a history of suicide attempt in the past 6 months or subjects who represent a significant risk of suicide in the opinion of the investigator.
4. Subjects who represent a significant risk of violence determined by the assessing clinician or PI, based on history, presentation, and the Buss-Perry Aggression Questionnaire ⁴⁸ or a rating of ≥ 5 on the BPRS hostility item.
5. Pregnant or nursing or positive urine pregnancy test.
6. Significant medical or neurological illness by history or physical exam, including seizure disorder, history of loss of consciousness lasting more than 30 minutes related to head trauma or intellectual developmental disorder.
7. Metal implants, such as a cardiac pacemaker, intra-cardiac lines, neurostimulator, medication infusion device, jewelry/piercings that cannot be removed, and/or any other metal in the body that cannot be removed.
8. Claustrophobia
9. A history of brain surgery
10. History of syncopal episode within the past 6 months
11. Cochlear implants
12. Skin disease at intended stimulation sites
13. The consumption of more than four alcoholic units within 24 hours before Intervention Visit 1 and 2, and any recreational drugs within 48 hours before Intervention 1 and 2

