5.3 Inclusion of Subjects Using Marijuana

The incidence of cannabis use psychosis patients in the US is estimated at 40% to 60% and a serious concern has been raised that excluding individuals who use cannabis may bias samples and make results less generalizable to clinical populations. There is no reason to expect a negative interaction between cannabis and PLIFUS. We will record past use of cannabis and urine toxicology screen results for cannabis at screening. Self-report of cannabis use will also be recorded at the beginning of each intervention visit. We will include this as a factor in our analysis to assess whether cannabis use influences response to PLIFUS. The determination of moderate or more severe cannabis use disorder will be based on the Diagnostic and Statistical Manual (DSM) 5 criteria.

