7.2.3 MRI Visit (Days -30 to -1)

- Obtain structural MRI scan for neuronavigation

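### Section 5.5.2 waives the urine pregnancy and drug tests for people screened in the CPEP or inpatient units, and no later visit is assigned to do them

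*Combined protocol and SAP*

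**What the plan says.** Section 5.1 item 5a requires a negative urine pregnancy test from participants of childbearing potential and adds that "all participants assigned female at birth regardless of childbearing potential will be required to submit a pregnancy test". Section 5.2 excludes on "Pregnant or nursing or positive urine pregnancy test" (item 5) and on "A positive urine toxicology screen" (item 1a, with exceptions for THC, tricyclics and prescribed benzodiazepines).

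Section 7.2.2 places the sample at the Screening Visit: "Obtain urine sample for pregnancy test and urine toxic screen". Eligibility is determined at the same visit.

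Section 5.5.2 allows consent and screening in the CPEP or the inpatient psychiatry units. It then states that "no screening laboratory procedures (urine drug screen, urine pregnancy screen) will take place for those who are screening in the CPEP"; the sentence goes on to include the inpatient units. After screening, "individuals who qualify, and who are judged by their clinicians to be safe and appropriate for participation", and who are still admitted, carry on in the study once they leave hospital. For Bellevue outpatients the same section does say where urine can be collected.

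**The concern.** The plan sets a universal safeguard and then, for one recruitment route, names the two tests that carry it as not done. It does not say when they are made up. The wording that follows speaks of people who qualify after screening, which can be read as meaning that screening is complete without the tests.

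Two things are at stake. First, the plan excludes pregnancy and tests even those without childbearing potential, but on this route nothing would detect an existing pregnancy before the MRI scans and sonication. Contraception from screening (item 5c) does not reveal a pregnancy already present. Section 5.8.1 lets the investigator withdraw someone whose exclusion was not recognized earlier, but no listed test would bring it to light. Second, the toxicology exclusion goes unverified in people recruited during acute psychiatric care.

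**Working it through.** There is no figure in the plan to reproduce. The check is a comparison of every place that mentions, or could be expected to mention, a urine or pregnancy test.

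1. **Requirement.** Item 5a: at least 1 pregnancy test per participant assigned female at birth. Exclusion 1a: a toxicology result for every participant.
2. **Visits that list a urine sample.** Sections 7.2.2 to 7.2.6 describe eight visits:
   - Screening (7.2.2): both tests listed.
   - MRI (7.2.3): the whole entry is "Obtain structural MRI scan for neuronavigation".
   - Intervention 1, 1B, 2 and 2B (7.2.4): rating scales, scans, PLIFUS or sham and safety assessments; no urine test.
   - Final (7.2.5) and Early Termination (7.2.6): no urine test.

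   Count: 1 of 8 visits lists the tests, and 0 of the 7 other than Screening.
3. **CPEP and inpatient route.** Section 5.5.2 removes the Screening tests: 1 − 1 = 0 scheduled pregnancy tests and 0 scheduled toxicology screens, against at least 1 of each required.
4. **Schedule of Events.** It has no row for either test at any visit. It marks randomization at the MRI Visit, so no listed step between a CPEP or inpatient screening and randomization supplies the results.
5. **Number affected.** The plan gives no count or expected share for this route. Among those who complete, it lies between 0 and 12, or between 0 and 12 + 4 = 16 if the three-session stage is run. Enrollment continues until 12 complete with usable imaging, so people treated who do not complete would come on top. The pregnancy test concerns only those assigned female at birth; the toxicology screen concerns everyone on the route.

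**The case against.** The best defense is that 5.5.2 limits where urine is taken, not whether it is taken. To qualify means to meet 5.1 and 5.2, and Section 4.1 sends only people who meet the criteria on to MRI. Section 7.2.2 contains no exemption. On this view, randomizing an untested participant would be a protocol deviation, not something the plan permits. That stands: a reader might infer that the eligibility rules are suspended or cannot be applied on this route, and the documents do not support that. What remains is that no visit, and no point before randomization, is assigned for the deferred test.

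The Schedule of Events is weak evidence by itself. It lacks a urine row even at Screening, where 7.2.2 requires the sample, and it omits Visits 1B and 2B. The point rests on 5.5.2 and the visit lists.

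Other stronger readings also go beyond the documents:

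- **Biased efficacy results.** A reader might infer that undetected drug use distorts the comparison with sham. The primary measure is the change from before to after sonication within a visit, with baseline in the model and each participant serving as their own control. A screening sample would not show use just before an intervention visit. Exclusion 13 governs that, for every recruitment route. The documents give neither size nor direction for any such effect.
- **Loss of the cannabis factor.** Section 5.3 relies on "urine toxicology screen results for cannabis at screening", but also on past use and on self-report at each intervention visit. One of three sources would be missing, and THC is not exclusionary under 1a.
- **A need to repeat pregnancy tests at both sessions.** The windows allow a Screening test up to 30 days old at the first session and 8 + 30 = 38 days old at the second. Those are extremes: Section 5.6 expects 14 to 21 days in all. With the final visit no earlier than Day 14, that puts screening at most about 21 − 14 = 7 days before the first session and about 7 + 8 = 15 before the second. The plan promises no repeat test.
- **Demonstrated fetal harm.** The documents identify no specific fetal hazard from sonication, and no MRI contrast is used.

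**Conclusion.** The concern holds as a gap in procedure. A stated exemption conflicts with a stated safeguard, and no step reconciles them. Following 5.5.2 and the visit lists to the letter could lead to an untested participant being randomized and sonicated.

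The size is 0 scheduled tests against at least 1 required, for an unknown number of participants that may be zero. Inclusion 4 narrows the route somewhat, since it requires an unchanged antipsychotic dose for 4 weeks before randomization, but unmedicated patients may also enter.

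The conclusion assumes that no separate instruction outside the protocol assigns the test and that hospital results are not already accepted in its place; the protocol mentions neither. It concerns participant safety and verification of eligibility. It changes no sample size, effect-size threshold or analysis. It does not show that anyone was treated untested. Because the contradiction is explicit and cheap to remove, it should be corrected.

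**What to change.** In 5.5.2 and 7.2.3, state that for participants screened in the CPEP or an inpatient unit, the urine pregnancy test (if assigned female at birth) and the urine toxicology screen are done after discharge, at the MRI Visit and before the scan, and that eligibility is confirmed from both results before randomization. Add a row for each test to the Schedule of Events: at Screening for everyone else, and at the MRI Visit for this group.

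The cost is one urine sample per such participant and a protocol amendment with IRB approval (Section 12.2). No visit is added, because the MRI Visit is already in person and, on this route, follows discharge. The drawback is a possible late screen failure after discharge. If results are not available the same day, the scan and randomization must wait for them; the plan does not say which assay is used.
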